**Multicenter double-blind placebo-controlled parallel group
randomized clinical study of efficacy and safety of Raphamin in the
treatment of acute respiratory viral infection in children aged 12-18
years**

Phase III

Sponsor	ООО «NPF «MATERIA MEDICA HOLDING»
Protocol number	MMH-407-003
Version date:	November 10, 2020
ClinicalTrials.gov Id:	NCT04918771

Protocol Summary

This document represents the protocol summary for the study on human patients. The study will be carried out in accordance with ICH GCP, Helsinki Declaration of World Medical Association, Rules of good clinical practice, approved by order of the Ministry of Health of the Russian Federation dated April 1, 2016 N 200n, , relevant requirements of the regulatory authorities as well as the study procedures.

Title of Study

Multicenter double-blind placebo-controlled parallel group randomized clinical study of efficacy and safety of Raphamin in the treatment of acute respiratory viral infection in children aged 12-18 years.

Phase: III

Sponsor: OOO «NPF "MATERIA MEDICA HOLDING», Moscow, Russia

Protocol No. MMH-407-003

Objective of the study

- To evaluate the efficacy and safety of Raphamin in the treatment of acute respiratory viral infection (ARVI) in children aged 12-18 years.

Endpoints

Primary endpoint

1. Time to resolution of ARVI^{1,2} symptoms (PCR-confirmed).

Secondary endpoints

1. ARVI severity (clinically diagnosed and/or PCR-confirmed; based on the area under the curve (AUC) results for the total severity index³ from days 1 to 6 of observation).
2. Percentage of patients with resolution of ARVI symptoms (clinically diagnosed and/or PCR-confirmed).
3. Time until resolution of ARVI symptoms, (clinically diagnosed and/or PCR-confirmed).
4. Percentage of patients with resolution of ARVI symptoms (PCR-confirmed).

¹Time from symptom onset at visit 1 until resolution of the disease symptoms.

Resolution of ARVI symptoms will be defined if temperature is $\leq 37.3^{\circ}\text{C}$ within 24 hours (without further increase during observation period) + lack/presence of systemic ARVI symptoms ≤ 2 .

² Based on a patient diary.

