Per protocol set. This sample includes all patients who completed the therapy as per the study protocol and completed all the scheduled visits. This set will be used for the **Per Protocol analysis (PP analysis)** of the study therapy efficacy. *PP set* will not include the patients with their data completely or partially invalid for analysis due to a protocol deviation.

⁵ Holder of license: OOO “NPF “MATERIA MEDICA HOLDING”, No. 70100045.

The list of deviations that may result in complete or partial invalidity of data is developed by a medical expert jointly with a biostatistician according to the study design.

The deviations that may result in partial or complete invalidation of the study subject's data.

1. Inappropriate distribution/supply of the study drug.
2. Prescription of prohibited therapy.
3. Increase or decrease in the study drug dosing by $\geq 25\%$.
4. Inability to assess the patient's compliance using the formula (e.g. loss of pack with the product).
5. Major discrepancies between source documents and CRF identified during monitoring or another authorized inspection.
6. Violation of the procedure of obtaining informed consent.
7. Non-compliance with the clinical study protocol procedures.
8. Inability to collect all the patient's data used for evaluation of the study endpoints⁶ (e.g. lack of records in source documents required for verification of inclusion/exclusion criteria, safety and efficacy criteria).
9. Any other protocol deviations covered by the term “major deviation”.

Evaluation of sample size

It is expected that out of 360 patients randomized 200 patients will complete the study per protocol⁷. Taking into consideration the expected screening failures, the informed consent should be obtained from 400 patients.

The sample size was assessed on the basis of the following rules and assumptions:

1. Statistical provisions.
 - 1.1 the power of the statistical tests “ $P = (1 - \beta)$ ” is assumed to be 80% (the probability of correct rejection of the null hypothesis is 0.8);
 - 1.2 the probability of a type I error “ α ” is allowed to be less than 5% (the probability of false acceptance of an alternative hypothesis is less than 0.05);
 - 1.3 the applied statistical tests for group comparisons are two-sided, unless stated otherwise;
 - 1.4 the sample size is calculated based on the assumptions on the expected effect declared in the primary endpoint of this protocol;

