⁶ If, considering the lack of some data in primary endpoint variable, the fact of reaching the primary endpoint by the patient can still be determined, the patient will be eligible for PP analysis (e.g. the diary lacks some records but the time of recovery can still be determined).

⁷ No more than 10% patients who signed PIS and ICF are expected to be screening failures for various reasons.

1.5 the ratio between the sample sizes of the study drug and placebo groups is 1:1 (1 study drug patient - 1 placebo patient);

1.6 statistical hypotheses: null and alternative hypotheses about the superiority of the study drug over placebo using the applied dosing regimen:

primary endpoint:

$$H_0: M_1 - M_2 = 0$$

$$H_a: M_1 - M_2 \neq 0$$

where : M_1 – average time to resolution of the symptoms in the Raphamin group,

M_2 – average time to resolution of the symptoms in the Placebo group.

Sample analysis will be performed according to the following formulas:

$$n_1 = kn_2$$

$$n_2 = \frac{(z_{\alpha/2} + z_{\beta})^2 * (1 + 1/k)\sigma^2}{\varepsilon^2}$$

where n_2 , n_1 is sample size in study drug and placebo groups, respectively;

$\varepsilon = M_1 - M_2$ is the time difference between Raphamin and Placebo groups;

k – coefficient of Raphamin/Placebo sample ratio ($k=1$);

σ - standard deviation;

$z_{\alpha/2}$ – tabular value of two-sided z-test for α ;

z_{β} – tabular value of one-sided z-test for β ;

1.7 Full sample size is determined using the formula:

$$N = N_{pp} / (1 - R_w),$$

where N – the final sample size;

N_{pp} – result of calculation in cl. 1.6, i.e. scheduled number of the patients completing the study per protocol;

R_w – withdrawal rate.

2. Assumptions on expected effects of the clinical study: The differences in duration of the disease between the groups is expected to be less than 1 day, with standard deviation in the groups of no more than 2.5^8 days.

Therefore, the number needed to compare study drug and placebo will be **200** patients for both groups. Given potential withdrawal of at least 50%⁹ patients ($R_w = 0.5$) during the study for

⁸Upper limit of confidence interval of standard deviation of the time to resolution of the symptoms for placebo group based on the results of study MMH-ER-009 "International multicenter double-blind placebo-controlled randomized parallel-group clinical study of efficacy and safety of Ergoferon in the treatment of acute respiratory viral infections in children".

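### When diary data are incomplete, footnote 6 states a route into the per-protocol set only for patients whose recovery can be determined, so entry in that subgroup can depend on the primary outcome

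*Combined protocol and SAP*

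**What the plan says.** All places are in the combined protocol and SAP.

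- **Statistical Analyses, Per protocol set.** Membership: "This sample includes all patients who completed the therapy as per the study protocol and completed all the scheduled visits". The set "will not include the patients with their data completely or partially invalid for analysis due to a protocol deviation". Recovery is not a condition of membership.
- **List of deviations under the same heading.** It is introduced as "The deviations that may result in partial or complete invalidation of the study subject's data". Item 8 is "Inability to collect all the patient's data used for evaluation of the study endpoints", and footnote 6 is attached to it.
- **Footnote 6.** When some primary-endpoint data are missing but "the fact of reaching the primary endpoint by the patient can still be determined, the patient will be eligible for PP analysis". The example is that "the diary lacks some records but the time of recovery can still be determined".
- **Endpoints, footnotes 1 and 2.** Resolution is taken from the diary and needs a normal temperature "without further increase during observation period", with few systemic symptoms left.
- **Evaluation of sample size.** The hypotheses compare average times to resolution. The 200 patients required are those completing per protocol.

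No section says how a patient without a documented recovery enters the analysis of time to resolution. Survival procedures are listed under Non-parametric criteria, but no censoring rule is given.

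**The concern.** An analysis set should be defined without reference to the outcome it is used to compare. Footnote 6 is a sensible attempt to avoid losing patients over trivial diary gaps, but it is written from the side of recovery. A patient with missing records and a datable recovery has a stated way in. A patient with the same gaps who was still ill has none, and that case is left to unspecified judgement.

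If those patients are left out, short times are kept and long times lost among incomplete diaries. Per-protocol times to resolution then look too short in each arm. If incompleteness also differs between arms, the treatment comparison shifts. The per-protocol count is the one on which the trial is sized, so its entry rule should be exact.

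**Working it through.** **1. The text, case by case.** Each patient below completed therapy and all visits. The wording allows two readings: literal (the endpoint was reached) and evaluability (whether it was reached can be determined).

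| Diary | Literal reading | Evaluability reading |
|---|---|---|
| Complete, recovered or not | eligible, footnote not needed | same |
| Gaps, recovery can be dated | eligible | eligible |
| Gaps mid-course, known still ill at the end | no stated route | eligible |
| Stops early while still ill | no stated route | no stated route |

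The evaluability reading repairs the third row but not the fourth.

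**2. The plan's own figures.** With the stated formula, SD 2.5 days, a 1-day difference, two-sided 5% and 80% power: n = (1.960 + 0.842)² × 2 × 2.5² / 1² = 98.1, so 99 per arm and 198 in total, against 200 stated. Withdrawal: 1 − 0.9 × (1 − 0.444) = 0.4996, and 400 × 0.9 × 0.556 = 200.2. The 50% allowance is made up of screening failures and discontinuations (10%) and PCR-negative patients (44.4%). No separate share is named for incomplete diaries.

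**3. Illustration with diaries that end early.** From the plan: SD 2.5 days. Assumed: gamma times T with means μ of 4 and 5 days; a share q of 10-30% of diaries ending at a time C, uniform on Days 1-7 and independent of T; an incomplete-diary patient is kept only if T < C.

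Let a = P(T < C) and m = E(T | T < C). Numerical integration gives a = 0.54 and m = 2.60 for μ = 4, and a = 0.40 and m = 3.27 for μ = 5. So 54% of incomplete-diary patients are kept in the faster arm and 40% in the slower.

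Kept mean = [(1 − q)μ + q·a·m] / [(1 − q) + q·a]. For μ = 5 and q = 0.2: (4.000 + 0.2 × 0.396 × 3.272) / (0.8 + 0.2 × 0.396) = 4.259 / 0.879 = 4.84.

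| q | Kept mean, μ = 4 (shift) | Kept mean, μ = 5 (shift) | Difference (true 1) |
|---|---|---|---|
| 10% | 3.92 (−0.08) | 4.93 (−0.07) | 1.01 |
| 20% | 3.83 (−0.17) | 4.84 (−0.16) | 1.01 |
| 30% | 3.74 (−0.26) | 4.75 (−0.25) | 1.01 |

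With no true effect (μ = 5 in both arms) and unequal incompleteness, the false difference is 4.927 − 4.844 = 0.083 day for 10% against 20%, and 4.927 − 4.749 = 0.178 day for 10% against 30%. The arm with more incomplete diaries looks faster.

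**4. Illustration with scattered gaps.** Here the only patients removed are those with gaps who are unrecovered at a fixed horizon H. With S the unrecovered share and R the restricted mean, the kept restricted mean is (R − q·H·S) / (1 − q·S). Take H = 7 days, means 4 and 5, q = 30%. The unrecovered shares are 11.8% and 19.1%, so 0.3 × 11.8 = 3.5 and 0.3 × 19.1 = 5.7 patients per 100 are removed. The difference moves from 0.864 to 0.838 day. For placebo means of 4-6 days and q of 5-30%, the shift stays under 0.03 day. At H = 14 days, fewer than 0.2 patients per 100 are removed.

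**The case against.** - **Exclusion of unrecovered patients is not stated.** Footnote 6 gives a sufficient condition, and the listed deviations only may invalidate data. A reader might infer that incomplete-diary patients enter only when recovered; the documents do not say so. This stands. What remains is that one outcome has a written rule and the other has none.
- **Per-protocol membership in general does not depend on recovery.** A reader might infer that it does. The set's definition has no such condition, and complete diaries enter whatever the outcome. This stands.
- **There is no conflict with the requirement to attend all visits.** A reader might see one, but footnote 6 qualifies item 8 and waives no visit. A child can miss diary entries and attend every visit. A child who leaves the study is excluded whatever the outcome, so early leaving does not act through this footnote.
- **A strict reading of footnote 1 would treat truncated diaries alike.** A diary that stops cannot show that temperature stayed down, so recovery could not be determined in either child and the selection would vanish. This has force, and it makes step 3 a reading of how the footnote might be applied. But the footnote's own example accepts a recovery time despite missing records and does not say how many records may be missing.
- **The bias in the treatment effect needs unequal incompleteness.** The arms are double-blind with the same tablet description and regimen, and nothing in the documents suggests unequal gaps. This stands, and the direction is not fixed in advance.

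**Conclusion.** The point holds for patients with incomplete primary-endpoint diary data: only those whose recovery can be determined have a stated route into the per-protocol set, so entry there can depend on the primary outcome. The Full Analysis Set, which serves the ITT analysis, does not use footnote 6.

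Under the step 3 assumptions, per-protocol means are about 0.07-0.26 day too short in each arm. The difference is almost unbiased with equal incompleteness and off by about 0.08-0.18 day with 10% against 20-30%, compared with the planned 1 day. The means, the incompleteness rates and the pattern of diary ending are assumptions; only the SD comes from the plan. If gaps are related to how ill the child is, both size and direction could differ. The documents do not support a claim that the trial's result is biased towards Raphamin.

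This is a cheap improvement worth making, not a fault that undermines the design.

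**What to change.** Reword footnote 6 so that eligibility is neutral to outcome. For example: *A patient who otherwise meets the per-protocol definition and has some missing diary records is eligible, whether or not recovery was reached, provided that a diary-completeness criterion is met. The criterion is fixed, and applied to each patient, before unblinding. Patients without documented recovery are censored at their last diary assessment.*

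The sponsor should choose the criterion; the documents give no basis for a particular threshold. The censored times can be handled with the survival procedures already listed under Non-parametric criteria (LIFETEST, PHREG). The requirement to complete therapy and all scheduled visits needs no change.

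Cost: one footnote. Some censored times will enter the per-protocol analysis, and a few recovered patients with very sparse diaries may leave it.

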14. Medical history of mental diseases of the patient or their parent(s)/adoptive parents.
15. Participation in other clinical trials for 3 months prior to enrollment in this study.
16. Patient's parents/adopters who are related to any of the on-site research personnel directly involved in the study or are an immediate relative of the investigator. 'Immediate relative' means husband, wife, parent, son, daughter, brother, or sister (regardless of whether they are natural or adopted).
17. The patient's parent/adopter who works for OOO "NPF "MATERIA MEDICA HOLDING" (i.e. the company's employees, temporary contract workers, designated officials responsible for carrying out the research or any immediate relatives of the aforementioned).

Criteria for Withdrawal or Termination

1. Screening failure.

2. Failure or refusal of the patient to follow the protocol.
3. The necessity to use medications not permitted in the study.
4. An adverse event requiring discontinuation of the study drug.
5. Patient's or his/her parent's/adopter's decision to withdraw early for lack of efficacy or other reasons.
6. Pregnancy.
7. Cases not stipulated in the protocol where the investigator decides that further participation may harm the patient.
8. Eligibility error.

Number of patients

It is planned to include 400 patients, 360 of them will be randomized which is expected to yield at least 200 patients (100 per Raphamin and Placebo groups) completing all the protocol procedures.

Interim analysis

The protocol does not schedule unblinded interim analyses. At the sponsor's decision, blinded interim analysis may be carried out to specify population parameters and potential further specification of sample size (increase only).

Treatment

Group I

Name of the medicinal product: Raphamin

Active ingredient: affinity purified antibodies to human interferon-gamma – 10 000 UMA*,
affinity purified antibodies to CD4 – 10 000 UMA,
affinity purified antibodies to β 2-microglobulin major histocompatibility complex class I – 10 000 UMA,
affinity purified antibodies to β 1-domain of major histocompatibility complex class II – 10 000 UMA

* UMA – Units of Modifying Activity.

Excipients: lactose monohydrate, microcrystalline cellulose, magnesium stearate.

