Schedule of study procedures

Procedure/Visit	Visit 1 (Day 1)	Visit 2 (Day 5±1)	Visit 3 (Day 7±1)	Visit 4 (Day 14±1)
Informed consent	+			
Registration of a study patient in the IVRS* and assignment of patient ID	+			
Complaints collection	+	+	+	
Medical history	+			
Concomitant diseases and conditions	+	+	+	+
Physical examination	+	+	+	
ARVI symptoms	+	+	+	
Concomitant therapy	+	+	+	+
SARS-CoV-2 rapid test	+			
Pregnancy test	+			
Inclusion/exclusion criteria	+			
Randomization	+			
Nasopharyngeal swabs for PCR	+			
Safety laboratory tests**	+		+	

Procedure/Visit	Visit 1 (Day 1)	Visit 2 (Day 5±1)	Visit 3 (Day 7±1)	Visit 4 (Day 14±1)
Study drug supply	+			
Antipyretic drug supply	+			
Evaluation of the study drug safety	+	+	+	+
Patient diary	+	+	+	+
Study drug accountability and return			+	
Treatment compliance			+	
Visit completion	+	+	+	+
Telephone survey				+
Study completion***				+

* Interactive voice/web response randomization system
 ** Laboratory tests include hematology, urinalysis, serum chemistry (total protein, C-reactive protein, glucose, total bilirubin, creatinine, ALT, AST, cholesterol). Performed with availability of signed PIS and ICF including the patient's consent for blood and urine sampling.
 *** In case of early withdrawal the procedure may be carried out at Visits 1, 2 or 3.

Statistical Analyses

SAS-[9.4].⁵ will be used for data processing and statistical calculations.

Samples

Total set: all enrolled patients who have signed ICF. This sample will consider all the recorded AEs, including those occurred prior to the study therapy.

Safety population: all included and randomized patients who received at least one dose of the study drug. This sample will be used for **analysis of the study treatment safety and tolerability**, as all adverse events identified after the study drug administration will be recorded.

Full Analysis Set. This sample includes all enrolled patients, except for those who met at least one of the following events:

- 1) non-compliance with inclusion / exclusion criteria;
- 2) patient did not take a single dose of the study drug;
- 3) lack of any data about the patient after administration of the study drug.

This sample, the most consistent with the “Intention-to-treat” principle, will be used for the **Intention-to-treat analysis (ITT analysis)** of the study therapy efficacy.

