⁹ This rate is composite: 10% patients will be screening failures or discontinue the study for other reasons specified in the relevant protocol section, in 44.4% remaining patients the diagnosis will not be confirmed by PCR. The rate was assessed based on PCR findings obtained in "Multicenter double-blind placebo-controlled randomized parallel-group study of efficacy and safety of MMH-407 in the treatment of acute respiratory viral infection" (MMH-407-001).

various reasons, at least **400** patients will be required to sign informed consent, with **200** subjects per group.

Statistical criteria

All the statistical calculations will be performed using two groups of statistical criteria:

- parametric – to obtain effective evaluations for parameters of random values, if the relevant conditions of applicability of methods/models are not violated (e.g. sphericity, normality, proportionality of risks, etc.);
- non-parametric – in any other cases.

Parametric criteria

The application of parametric criteria will be accompanied by a check of models for applicability (e.g. Kolmogorov-Smirnov test, Shapiro-Wilk test, etc.).

The following parametric tests and approaches are to be used:

1. To evaluate the differences of continuous variables obtained in one group at two different visits – Student's test for matched samples.
2. To evaluate the temporal dynamics of the compared indicators – analysis of variance (ANOVA) or covariance (ANCOVA) in the modification with repeated measures.
3. In case of multiple comparisons between the groups will apply a variety of corrections for multiplicity (Dunnett, Tukey, Scheffe, Holm adaptive test), etc.
4. In case of abnormal data distribution, approaches with the Generalized Linear Models and / or Mixed Linear Models will be used.
5. Selection of the type of distribution, specification of the factor and covariance structures of the model will be made using fit-statistics such as AIC¹⁰ (Akaike information criterion).

To perform the above-mentioned statistical tests and techniques, it is assumed that the following SAS procedures are used:

- UNIVARIATE – check for normality of the compared distributions;
- CORR, MEANS – calculation of descriptive statistics;
- TTEST – Student t-test with all the modifications;
- GLM – analysis of General Linear Models for studying temporal dynamics (ANOVA, ANCOVA);
- GENMOD – analysis of Generalized Linear Models;
- MIXED – analysis of Mixed Linear Models.

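### The 200 per-protocol completers leave no allowance for loss after randomisation, because screening failure uses up the 10% and PCR non-confirmation alone takes 360 to 200

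*Combined protocol and SAP*

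**What the plan says.** The sample size is set on the per-protocol set. Item 1.7 of Evaluation of sample size inflates N_pp, defined as the "scheduled number of the patients completing the study per protocol", by 1/(1 − R_w), with R_w = 0.5. N_pp is 200 for both groups.

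The flow is given in the same section: "It is expected that out of 360 patients randomized 200 patients will complete the study per protocol", and then "Taking into consideration the expected screening failures, the informed consent should be obtained from 400 patients". Footnote 7 adds: "No more than 10% patients who signed PIS and ICF are expected to be screening failures for various reasons". The Number of patients section gives the same chain of 400, 360 and at least 200.

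Footnote 9 explains R_w as a composite. First, "10% patients will be screening failures or discontinue the study for other reasons specified in the relevant protocol section"; then 44.4% of those remaining are not confirmed by PCR.

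Elsewhere the protocol expects losses after randomisation:

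- Criteria for Withdrawal or Termination lists "An adverse event requiring discontinuation of the study drug".
- The study-completion footnote to the Schedule of study procedures says "In case of early withdrawal the procedure may be carried out at Visits 1, 2 or 3".
- The Per protocol set definition requires completed therapy and all scheduled visits, followed by nine kinds of deviation that can invalidate a patient's data.

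No rate is attached to any of these.

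**The concern.** Footnote 9 lets one 10% figure cover two different things: failure at screening, which happens before randomisation, and discontinuation, which can happen after it. The counts do not share it out. The step from 400 to 360 is attributed to screening failure only and takes all 10%. The step from 360 to 200 equals the PCR rate and nothing else. Discontinuation is named in the footnote but has no patients assigned to it, and per-protocol exclusion for a deviation is not mentioned in the rate at all.

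The 80% power rests on 200 per-protocol completers. If the plan can reach that number only with no other loss, the stated power is a best case. A reader cannot see this from the text, and the sponsor has no stated loss rate against which to judge whether the optional blinded review should increase the sample.

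**Working it through.** **Inputs from the documents** (Evaluation of sample size, with its footnotes): two-sided α 0.05, power 80%, SD at most 2.5 days, 1:1 allocation, R_w 0.5, a first component of 10%, and a PCR non-confirmation rate of 44.4%.

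**Assumptions.** The difference is taken as 1 day. The text says "The differences in duration of the disease between the groups is expected to be less than 1 day", but 1 day is the value that reproduces the stated number. Post-randomisation loss L is taken as 5% or 10% and as independent of PCR status, because the documents give no rate.

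**Reproducing the plan's figure.** n per group = (1.960 + 0.842)² × 2 × 2.5² / 1² = 98.11, or 196.2 in total. Rounded up this is 99 per group, 198 in total, which agrees with the stated 200. Then 200 / (1 − 0.5) = 400.

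**Reproducing the flow.**

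- 400 × 0.90 = 360 randomised, which uses the full 10%.
- 360 × (1 − 0.444) = 200.2.
- Composite R_w = 1 − 0.90 × 0.556 = 0.4996.
- Lost after randomisation: 360 − 200 = 160, and 160/360 = 44.4%, which is the PCR rate exactly.

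If part of the 10% were discontinuation, more than 360 would be randomised. At 5% screening failure, for example, 400 × 0.95 = 380. That disagrees with the stated 360.

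**Room for loss.** By the protocol's formula, 1 − 196.22/200.16 = 2.0%. The t-test requirement is 99.08 per group, 198.2 in total, which leaves about 1.0%.

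**Effect of an assumed loss.** Remaining patients = 200.16 × (1 − L); R_w = 1 − 0.9 × (1 − L) × 0.556; power = Φ(δ / (σ√(2/n)) − 1.960), with n per group. Power is computed at rounded totals of 200, 190 and 180.

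| Loss L | Patients left | R_w | Power, 1 day (normal) | Power, 1 day (t-test) | Power, 0.9 day (normal) |
|---|---|---|---|---|---|
| 0% | 200.2 | 0.500 | 80.7% | 80.4% | 72.1% |
| 5% | 190.2 | 0.525 | 78.7% | 78.3% | 69.9% |
| 10% | 180.1 | 0.550 | 76.5% | 76.1% | 67.5% |

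For example, at 180 patients: 1 / (2.5 × √(2/90)) = 2.683; 2.683 − 1.960 = 0.723; Φ(0.723) = 76.5%.

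**Sensitivity to the SD.** Power at 1 day is still 80% with 190 patients if the true SD is no more than 2.46 days, and with 180 patients if it is no more than 2.39.

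**Chance variation in the PCR-positive count.** SD = √(360 × 0.556 × 0.444) = 9.4, so the 95% range is about 182 to 219. A 5–10% loss is of similar size, but it lowers the expected number instead of scattering around it.

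**The case against.** The best defence is that footnote 9 does mention discontinuation, and footnote 7 makes 10% a ceiling for screening failure. On that view the plan considered dropout and only allocated a composite rate loosely. No sum is wrong, and the passages are not in strict contradiction. That is fair as to wording. It does not rescue the counts: 360 randomised is fixed in two sections, and from 360 to 200 the PCR rate is the only loss.

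The margin also depends on method: about 2% by the unrounded formula, about 1% by the t-test or with 99 per group, and none if the t-test figure is rounded up to 100 per group. This stands, and it does not help the plan, since every version is close to zero.

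Several points limit the consequence, and they stand too. The SD of 2.5 is an upper confidence limit (footnote 8). Treatment lasts only 5 days. Footnote 6 keeps patients with diary gaps when recovery time can still be determined. The full analysis set can keep patients who stop early but have data after dosing. The Interim analysis section allows a blinded, increase-only review, though only at the sponsor's decision. The reading of the difference also matters more than the loss: at 0.9 day, power is 72.1% even with 200 patients.

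Finally, raising R_w while keeping N_pp = 200 would require more than 400 consents under item 1.7. This is a sound caution about the correction: R_w, the analysable number and the power have to be restated together.

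**Conclusion.** The point holds. The plan reaches 200 per-protocol completers only by assuming, without saying so, that no PCR-positive patient is lost or excluded after randomisation. The protocol's own withdrawal criteria, visit schedule and per-protocol rules say otherwise. At the planning values the room for loss is about 2% by the protocol's formula and about 1% by the t-test. An assumed 5% or 10% loss lowers power from 80.7% to 78.7% or 76.5%, a drop of about 2 to 4 points.

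These sizes rest on a difference of exactly 1 day, an SD of 2.5 days, a PCR-positive rate of 55.6%, and loss rates that are assumed because the documents give none. The effect is modest. It should be fixed because the stated sample size and power are not supported as written and the correction is cheap.

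**What to change.** In Evaluation of sample size and footnote 9, give three separate rates: screening failure before randomisation, discontinuation or per-protocol exclusion after randomisation, and PCR non-confirmation. For 360 randomised, restate R_w, the expected number analysable per protocol and the resulting power together, and show the difference used (1 day, if that was meant) and the SD. The 80% in item 1.1 should then be described consistently with the restated power.

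Two editorial points in the same place: withdrawal is given as a minimum of 50% beside a minimum of 200 completers, and the closing figure of 200 subjects per group counts consented patients. It should read 200 consented and 180 randomised per group.

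The cost is wording and one recalculation. No extra patients are needed, but the stated power becomes about 2 to 4 points lower at an assumed 5–10% loss. If the sponsor prefers to keep 200 completers instead, 200 / (0.556 × 0.95) gives 379 randomised at 5% loss, or 421 consented after dividing by 0.9. At 10% loss the figures are 400 randomised and 445 consented.
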